8.3.1 Non-inferiority hypotheses test

Non-inferiority will be tested using a one-sided type I error of 2.5% (equivalently a two-sided 95% confidence interval [CI]):

$$H_0: \theta \geq \Delta \text{ vs. } H_1: \theta < \Delta$$

Non-inferiority will be concluded if the upper bound of the two-sided 95% CI for θ is strictly less than Δ (3.0 weeks).

8.3.2 Analysis populations

In non-inferiority trials, intention-to-treat (ITT) analyses may be biased toward non-inferiority due to treatment cross-over and non-adherence. We intend to analyze both the per-protocol (PP) and ITT populations. The primary non-inferiority analysis will be performed in the PP population. A supportive analysis will be performed in the ITT population. Non-inferiority will be considered robust if conclusions are consistent in both PP and ITT analyses. We suspect very few cases will cross over. We suspect to find similar results in both groups and a discrepancy would warrant close examination of the results.

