8.3.4 Intention-to-Treat (ITT) population

Intention-to-Treat (ITT) population will include all randomized participants analyzed according to their randomized treatment allocation, regardless of the treatment actually received, protocol deviations, or subsequent withdrawal from the assigned intervention. Participants will contribute all available follow-up data collected until withdrawal of consent or study end. The ITT population will be used for supportive analyses of the primary endpoint and for key secondary outcomes, complementing the primary Per-Protocol analysis in this non-inferiority trial.

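### Non-inferiority can be declared on the per-protocol set alone, even when the interval in all randomised children crosses 3.0 weeks; requiring both sets is a cheap improvement

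*Protocol*

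**What the plan says.** Protocol 8.3.1 gives the decision rule: "Non-inferiority will be concluded if the upper bound of the two-sided 95% CI for θ is strictly less than" the 3.0-week margin. It does not say in which analysis set. Section 8.3.2 supplies the set: "The primary non-inferiority analysis will be performed in the PP population. A supportive analysis will be performed in the ITT population". ITT is supportive there, and 8.3.4 repeats this: "The ITT population will be used for supportive analyses of the primary endpoint and for key secondary outcomes".

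On agreement between the sets, 8.3.2 says: "Non-inferiority will be considered robust if conclusions are consistent in both PP and ITT analyses". On disagreement it asks only that the results be examined closely. No section makes the ITT result a condition for the claim.

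Sections 8.3.3 and 8.3.3.1 define PP by what happens after randomisation. A child leaves the set for receiving the other device, for having no intramedullary fixation, for a cast duration more than 7 days off plan (with an exemption for documented medical reasons), for a healing-related reoperation before union, or for films too sparse to define the healing interval.

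**The concern.** Section 8.3.2 justifies PP by noting that cross-over and non-adherence can bias ITT towards non-inferiority. That is a good reason to require PP to pass. It is not a reason to let PP decide alone, particularly as the same section expects very few cross-overs.

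Selection after randomisation can bias in the opposite direction. Reoperation before union is tied to the endpoint itself. Sections 2 and 9.3.3 name the flexibility of BIN as a possible cause of delayed union and re-angulation, so exclusions could fall unevenly on the BIN arm. Section 8.2.4 describes 3.0 weeks as the largest acceptable delay. A positive claim alongside an all-randomised interval that crosses that limit would be hard to defend, yet the stated rule produces one.

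**Working it through.** **Planning figures.** Inputs from 8.2: SD 3 weeks, margin 3 weeks, one-sided alpha 0.025, power 90%, 10% inflation. A true difference of 0 is implied, not stated.

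n = 2 × (1.960 + 1.282)² × 3² / 3² = 21.01, rounded up to 22 per group; 22 / 0.9 = 24.4, rounded up to 25. Both match the protocol. With the 30 per group to be enrolled, power is 97.2% before exclusions.

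**How the sets can disagree (assumed figures).** Take 30 per arm, a PP difference of 1.2 weeks, and 4 BIN and 1 TEN children excluded who heal 6 weeks later than the rest.

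- PP: 1.2 + 2.006 × 3 × √(1/26 + 1/29) = 2.83 weeks. Non-inferior.
- ITT difference: 1.2 + 6 × (4 − 1)/30 = 1.8 weeks. The late healers raise the variances to about 13.3 (BIN) and 10.2 (TEN), so the upper limit is 1.8 + 2.002 × √(13.3/30 + 10.2/30) = 3.57 weeks. The margin is crossed.

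The stated rule declares non-inferiority here.

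**False declarations at the margin.** Set-up: TEN healing times Weibull with mean 8 and SD 3 weeks (8.2.2), BIN scaled to a median delay of exactly 3.0 weeks, the protocol's film schedule, an interval-censored Weibull model and a likelihood-ratio test at one-sided 2.5%. PP drops the three slowest BIN children and three random TEN children. Ranges cover separate simulations of 800 to 2,500 trials.

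| Excluded BIN children in ITT | PP alone | Both sets required |
|---|---|---|
| Full healing times kept | 9.0-10.3% | 2.2-2.7% |
| Censored at week 10 | 9.0-9.8% | 4.4-4.6% |
| Censored at week 6 or earlier | 9.0-10.0% | 7.9-10.0% |

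Simulation error is about 1 point for the larger entries: √(0.09 × 0.91 / 800) = 1.0%.

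With one or two slow BIN children dropped and full times kept in ITT, PP alone gives 4.2% and 6.6%, against 2.3% for both sets. With one dropped and censored early, both rules give 4.5%.

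**When exclusions are harmless.** With 30 per group, no true difference and exclusions unrelated to healing (normal model, 100,000 trials), PP passes while ITT fails in 0.3% of trials at 5% exclusion per arm and 0.4% at 10%.

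**Cost in power.** In the same normal model, power is 95.9% for PP alone and 95.6% for both sets at 5% exclusion, and 94.9% and 94.5% at 10%. In the Weibull model with three random exclusions per arm it is 94.2% and 93.6% in one run (a loss of 0.6 points), and 93.2% and 93.0% in another.

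**The case against.** The strongest objection is that the listed exclusions do not clearly remove slow healers from PP while ITT keeps their late healing times. Sections 6.2.17.2 and 8.3.8 censor reoperated children at the last film before the event. Children without a film showing union are right-censored too (8.3.10). A cast prolonged for slow healing may fall under the medical exemption. Receiving the wrong device or no fixation would normally arise at surgery, before healing is seen. This largely stands. A reader might infer that the PP-only rule carries a false-declaration rate near 10% and that requiring both sets restores about 2.5%. The documents do not support that as a general statement: under their own censoring rules, early censoring leaves little or no protection.

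A reader might also equate the planned 10% loss, three children per arm, with loss of the three slowest BIN healers. Section 8.2.6 does not say so: it splits the 10% into about 5% loss or withdrawal and about 5% intercurrent events. Section 7.2.6.4 anticipates reoperation in 0.1-0.5%, at most 30 × 0.005 = 0.15 children per arm.

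Third, the protocol is not without safeguards. It plans both analyses, links the word robust to their agreement, and adds a sensitivity analysis that counts healing-related reoperation as not united (8.3.8). That is true, but none of these binds the decision.

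Finally, a prespecified single primary set with a stated reason is a legitimate choice and contradicts nothing. That is fair. The weakness is the stated consequence when the two sets disagree.

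**Conclusion.** The point holds as a weakness in the decision rule. As written, a PP pass suffices and an ITT interval crossing 3.0 weeks does not stop the claim, although PP membership depends on events after randomisation that are partly related to the outcome.

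The size of the benefit from requiring both sets is uncertain. It is substantial where excluded children's healing is still observed in ITT, partial where they are censored late, and small or nil where they are censored by week 6. The 9-10% figure is a worst case that assumes exclusion of exactly the slowest BIN children and a true delay at the margin; the protocol gives no exclusion rates by arm. With balanced exclusions unrelated to healing, conflict between the sets is rare.

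The stricter rule can never declare non-inferiority more often than PP alone, because it adds a condition. It does not cure the informative censoring of reoperated children; for that, the 8.3.8 sensitivity analysis remains relevant.

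**What to change.** State in 8.3.1 and 8.3.2: *Non-inferiority is concluded only if the upper limit of the two-sided 95% CI for BIN minus TEN lies below 3.0 weeks in the PP population and also in the ITT population; if the two disagree, non-inferiority is not concluded.* Align the supportive role given to ITT in 8.3.4 with this.

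The change takes a sentence or two and no new analysis. No alpha adjustment is needed because both tests must succeed. The cost under random exclusions is at most about 0.6 points of power, which stays at about 93-94.5% with 10% excluded, above the planned 90%, so no extra children are needed. Keep the 8.3.8 sensitivity analysis and report it beside the two main results.

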8.3.3 Per-Protocol (PP) population

Per-Protocol (PP) population will include all randomized participants who

- (i) received the allocated surgical intervention (BIN or TEN) as randomized
- (ii) had no major protocol deviations expected to materially affect fracture healing assessment
- (iii) contributed sufficient radiographic follow-up to define interval-censored time to union.

8.3.3.1 Major protocol deviations

Major protocol deviations resulting in exclusion from the PP population will include:

- (1) implantation of a non-allocated device or cross-over to the alternate trial implant
- (2) failure to undergo intramedullary fixation after randomization
- (3) major deviations in post-operative immobilization that alter the treatment package (e.g., cast duration differing by more than ± 7 days from the planned duration, unless medically indicated and documented)
- (4) healing-related reoperation prior to reaching the radiographic healing threshold (e.g., revision fixation for loss of reduction or refracture)
- (5) missing radiographic assessments such that the healing interval cannot be determined (e.g., absence of any post-operative radiograph beyond the initial post-operative imaging or missing consecutive assessments preventing interval definition).

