6.2.17 Premature study termination

A participant's involvement in the study may end prematurely (discontinuation of study participation) and/or the participant may discontinue the allocated treatment while remaining in study follow-up.

Reasons may include, but are not limited to:

- Withdrawal of informed consent (for study participation and/or use of data)
- Protocol deviation/violation with potential impact on participant safety or data integrity
- Refracture and/or reoperation (e.g., infection, implant-related complication)
- Investigator's decision (e.g., noncompliance with study procedures, safety concerns)
- Sponsor's decision (e.g., early study termination, safety signal, or regulatory request)
- Lost to follow-up
- Death

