8.2.2 Standard deviation

Due to limited evidence on the exact healing times of forearm fractures in children, the values are based on our pilot study, available literature [14,56] and our clinical expertise. In our pilot study of 18 fractures median time to healing with an mRUS of at least 11, was 8 weeks. We estimate that fractures heal to an mRUS of ≥ 11 at an average of 8 weeks with a SD of 3 weeks.

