8.3.5 Testing for superiority

If non-inferiority is established, superiority of BIN versus TEN will be assessed using the same confidence interval framework. Superiority will be concluded if the upper bound of the 95% CI for (BIN – TEN) is < 0 weeks.

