8.3.8 Intercurrent events

Healing-related reoperation (e.g., for refracture, deep infection requiring implant removal, or nonunion) will be treated as an intercurrent event for the primary endpoint. In the primary analysis, participants will be censored at the last radiographic assessment prior to the intercurrent event. Sensitivity analyses will assess robustness using conservative assumptions, including classifying healing-related reoperation as not united within the follow-up window.

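### The primary per-protocol set excludes children reoperated before union, while two other sections keep and censor them; the exclusion selects on an outcome of the implant and should go

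*Protocol*

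**What the plan says.** Section 8.3.2 of the protocol: "The primary non-inferiority analysis will be performed in the PP population". ITT is supportive, and agreement of the two sets makes a non-inferiority finding robust.

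Section 8.3.1 gives the decision rule: "Non-inferiority will be concluded if the upper bound of the two-sided 95% CI for" the BIN minus TEN difference is below 3.0 weeks.

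Section 8.3.3.1 lists the major deviations that remove a child from PP, among them "4) healing-related reoperation prior to reaching the radiographic healing threshold (e.g., revision fixation for loss of reduction or refracture"). Item (5) of that list removes children whose missing films prevent the healing interval from being determined.

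Section 8.3.8 treats healing-related reoperation as an intercurrent event: "In the primary analysis, participants will be censored at the last radiographic assessment prior to the intercurrent event". It adds a sensitivity analysis that counts such children as not united, without naming a population or a time horizon. Section 6.2.17.2 gives the same censoring rule for reoperation and refracture, unless the SAP names the event as a competing event.

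Two related places matter. Section 8.3.5: "If non-inferiority is established, superiority of BIN versus TEN will be assessed using the same confidence interval framework"; no population is named. Section 6.2.17 lists, among possible reasons for premature termination or discontinuation, "Refracture and/or reoperation (e.g., infection, implant-related complication").

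**The concern.** The protocol gives two incompatible instructions for the same children in the same analysis. Once item (4) has been applied, no child reoperated before union is left in the primary set to be censored. An analyst could follow either rule and claim to follow the protocol.

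Item (4) also differs in kind from items (1) to (3). Those ask whether the allocated treatment package was delivered. A revision for loss of reduction or refracture is something that happens after the package was delivered as planned; it is a result of treatment. Section 2 gives the lower stability of the more flexible BIN as the reason to fear delayed union, and section 9.3.3 says re-angulation may be more frequent with BIN. If such failures do occur more often with BIN, the set that decides the trial is selected in the direction that makes non-inferiority easier to conclude.

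**Working it through.** **1. The rules side by side, for a child revised before reaching the healing threshold**

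| Section | Status of the child |
|---|---|
| 8.3.2 with 8.3.3.1 item (4) | not in the primary analysis |
| 8.3.8 | in the primary analysis, censored at the last film before the event |
| 6.2.17.2 | kept, censored at the last evaluable film before the event |
| 8.3.4 (ITT, supportive) | kept, contributes all available follow-up |

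The first two rows exclude each other.

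**2. The plan's own sample size**

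Inputs: one-sided alpha 0.025 (8.2.3), power 90% (8.2.1), margin 3 weeks (8.2.4), and healing "at an average of 8 weeks with a SD of 3 weeks" (8.2.2). A true difference of 0 is assumed, as none is stated.

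n per group = 2 × (1.960 + 1.282)² × (3/3)² = 21.01, rounded up to 22. With 10% inflation, 22/0.90 = 24.4, rounded up to 25. Both figures reproduce; 30 per group are to be enrolled.

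**3. How many children are affected**

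- Section 7.2.6.4, reoperation for any reason 0.1-0.5%: 60 × 0.001 = 0.06 to 60 × 0.005 = 0.3 children.
- Section 8.2.6, about 5% intercurrent events affecting the primary endpoint: 60 × 0.05 = 3 children.

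**4. Effect on the conclusion, under assumed failure rates**

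Simulation with 30 per arm and 300 trials per scenario. Healing times are Weibull with mean 8 and SD 3 weeks (shape 2.90, scale 8.97, median 7.91). Films are at 2, 4, 6, 8, 10, 12, 24, 52 and 104 weeks. The analysis is an interval-censored Weibull accelerated failure time model with a delta-method 95% CI for the difference in medians. Assumptions not in the protocol: the failure rates, reoperation at 2-8 weeks, failures unrelated to underlying healing time, and equal healing in all other children. That last assumption makes the difference after exclusion close to zero by construction. Monte Carlo error is up to about 3 points.

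Each cell gives the mean estimated difference in weeks and the share of trials concluding non-inferiority.

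| Failures BIN / TEN | Exclude | Censor | Not united by 12 wk | Not united by 24 wk |
|---|---|---|---|---|
| 0% / 0% | 0.06; 97% | 0.06; 97% | 0.06; 97% | 0.06; 97% |
| 5% / 5% | 0.07; 97% | 0.07; 97% | 0.03; 94% | -0.06; 64% |
| 10% / 0% | 0.07; 96% | 0.12; 94% | 0.82; 72% | 2.85; 10% |
| 20% / 0% | 0.06; 95% | 0.16; 93% | 1.59; 36% | 5.19; <1% |

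Exclusion and censoring give nearly the same answer. Removing the contradiction alone therefore does not remove the possible bias, because censoring at failure is itself informative.

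**5. Why the 24-week column should not be taken at face value**

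If 10% of BIN children never united and the rest healed as assumed, the BIN median m solves 0.90 × F(m) = 0.5. So F(m) = 0.5556 and m = 8.97 × (-ln 0.4444)^(1/2.90) = 8.35 weeks. The shift is 8.35 - 7.91 = 0.44 week. At 20%, F(m) = 0.625, m = 8.91 and the shift is 1.0 week. The fitted 2.85 and 5.19 weeks are far larger. A few children held unhealed to 24 weeks, more than 5 SD above the mean ((24 - 8)/3 = 5.3), distort the Weibull shape and scale.

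**The case against.** The strongest reply is that the problem is small and already covered. Section 7.2.6.4 expects well under one reoperation in 60 children, all pilot fractures healed (4.6), and section 9.3 expects BIN complications to be comparable or lower. The ITT analysis, the not-united sensitivity analysis, complication reporting and the safety review in 19.1 would all still show these children. A discrepancy between PP and ITT calls for close examination (8.3.2).

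Much of this stands. At 0.1-0.5% the choice of rule hardly matters, and at equal 5% rates exclusion and censoring agree. It does not answer the contradiction. Nor does it change the fact that the decision rule is applied to the PP set, with the other analyses only supportive.

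Several stronger readings are tempting and are not supported:

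- That the plan hides BIN's inferiority. The children are absent from the decisive analysis only, and bias towards BIN needs more failures with BIN. Section 9.3.3 makes that plausible, says casting mitigates it, and gives no rate.
- That BIN failures of 10% would mean a delay of nearly 3 weeks. That figure is largely a fitting artefact of the 24-week horizon, as step 5 shows.
- That censoring throws the child away. A censored child still contributes being unhealed up to the last film. The valid objection is that the censoring is informative.
- That ITT is certain to repeat the problem. Section 8.3.8 limits its rule to the primary analysis, and 8.3.4 uses all available follow-up. Section 6.2.17.2 states its censoring rule without naming a population, so ITT handling is unclear.
- That reoperated children must leave the study. Section 6.2.17 gives possible reasons and allows stopping treatment while staying in follow-up.
- That superiority will be tested in PP. Section 8.3.5 does not say so.

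**Conclusion.** The contradiction between 8.3.3.1 item (4) and sections 8.3.8 and 6.2.17.2 is certain and concerns who is in the primary analysis. Item (4) is also wrong in kind, since it selects on an outcome of the allocated implant. The size of any bias is not established. It is negligible at the protocol's 0.1-0.5% reoperation rate, and possibly material at or above its roughly 5% allowance if failures are unequal between arms.

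Under the assumed 10% against 0%, exclusion or censoring leads to non-inferiority in 96% or 94% of trials, against 72% when failures count as not united by 12 weeks. These figures rest on the assumptions in step 4 and illustrate sensitivity; they do not predict the trial.

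A reader might infer that the not-united rule at 24 weeks should become primary. The figures do not support that: with equal 5% failures in both arms it concludes non-inferiority in about 64% of trials, against planned power of 90%.

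**What to change.** 1. Delete item (4) from 8.3.3.1, so that children reoperated before union stay in the primary set under the rule in 8.3.8. Align 6.2.17.2 with it.
2. State that item (5) does not remove unhealed children who have follow-up films; they are right-censored.
3. Run the not-united analysis of 8.3.8 in both PP and ITT, with its horizon fixed in advance. Do not describe non-inferiority as robust if this analysis or the ITT analysis disagrees with the primary result.
4. Do not make right-censoring at 24 weeks the primary rule without justifying the horizon and rechecking power.
5. Name ITT as the population for the superiority test in 8.3.5.
6. State in 6.2.17 that children with refracture or reoperation remain in study follow-up where consent allows.

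The cost is protocol wording before the first patient and one more planned analysis. Items 1 to 3, 5 and 6 need no extra patients or scheduled visits. Making a not-united rule primary is a choice of estimand and could need a larger sample.

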8.3.3.2 Minor protocol deviations

Minor deviations (e.g., visit timing deviations within predefined windows) will not lead to PP exclusion and will be handled analytically through the interval-censored time-to-event framework.

8.3.4 Intention-to-Treat (ITT) population

Intention-to-Treat (ITT) population will include all randomized participants analyzed according to their randomized treatment allocation, regardless of the treatment actually received, protocol deviations, or subsequent withdrawal from the assigned intervention. Participants will contribute all available follow-up data collected until withdrawal of consent or study end. The ITT population will be used for supportive analyses of the primary endpoint and for key secondary outcomes, complementing the primary Per-Protocol analysis in this non-inferiority trial.

8.3.5 Testing for superiority

If non-inferiority is established, superiority of BIN versus TEN will be assessed using the same confidence interval framework. Superiority will be concluded if the upper bound of the 95% CI for (BIN – TEN) is < 0 weeks.

8.3.6 Interval-censored union times

Because union is assessed only at scheduled radiographic visits (every 2 weeks), the true time to union is interval-censored (occurring between the last assessment without union and the first assessment with union). The primary analysis will use an interval-censored time-to-event model. A parametric

accelerated failure time model (Weibull) will be used to estimate the treatment effect and its confidence interval on the pre-specified estimand scale (e.g., time ratio/acceleration factor, and/or model-based difference in median time to union in weeks). Sensitivity analyses will repeat the primary analysis using alternative parametric distributions (e.g., log-normal/log-logistic) to assess robustness.

